This study will enroll 292 patients and equally allocate into 3 groups. All these calculations utilize an estimate of standard deviation of change based on the conservation of correlation of 0.5 between pre and post measurements within each group, based on Analysis of Variance (ANOVA) with two-sided Type I error of 5%. For the first study aim, the difference in the mean change of zBMI and %BMIp95 between baseline, 6 months, and 18 months across App+Coach, App, and Clinic, this study has at least 83% power to detect the effect size of 0.244 with the variance of the group means of 0.0003 for the mean change of zBMI and at least 89% power to detect the effect size of 0.263 with the variance of the group means of 2.903 for the mean change of %BMIp95. For the second study aim, the difference in zBMI and %BMIp95 mean change between App+Coach and Clinic, based on two sample t-test with two-sided Type I error of 5%, this study has 88% to detect an effect size of 0.580 corresponds to the mean difference of pre and post change in zBMI at least 0.040 standard deviation between the two groups and a 92% power to detect an effect size of 0.625 corresponds to the mean difference of pre and post change in %BMIp95 at least 4.08 percent between the two groups. For the third study aim, the difference in zBMI and %BMIp95 mean change between App+Coach and App, based on two sample t-test with two-sided Type I error of 5%, this study has 71% power to detect an effect size of 0.464 corresponds to the mean difference of pre and post change in zBMI at least 0.032 standard deviation between the two groups and a 68% power to detect an effect size of 0.452 corresponds to the mean difference of pre and post change in %BMIp95 at least 2.80 percent between the two comparison groups. Assuming 20% dropout rate, this study will achieve the desired study power of 80% for study aim 1 and 2. (nQuery + nTerim 4.0 and Stata/SE 15.1).

Statistical Analysis

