Statistical analysis: All statistical analyses were conducted in accordance with the planned study protocol.¹⁹ We estimated that 180 participants (60 in each group) would provide 89% power ($\alpha = 0.05$, 2 sided), to detect an effect size of 0.29 which corresponds to a difference of 4.0% %BMIp95 between the three groups. Analyses followed principles of intention-to-treat (ITT) and were performed in nQuery + nTerim 4.0 and Stata/SE 17 (StataCorp, College Station, TX). A two-sided significance level of 0.05 was utilized throughout the analyses. Our analysis approach is based under the assumption that data are missing at random, therefore, imputation using last observation was carried forward, and multiple imputation based on logistic regression model (for BEDS-7 scores only) were utilized to account for missing data. Results from the ITT analysis using imputation were compared as per protocol analysis with completed data. For all outcomes a per-protocol analysis was conducted for: full-program (completed full 24-week intervention period), pre-COVID (completed 24-week intervention prior to 3/15/2020), and during COVID (completed 24-week intervention after 3/16/2020). In addition, to account for impacts of the intervention dosage received on each primary outcome measure we conducted an analysis of participants who were adherent to at least 80% of the prescribed intervention modalities versus those who were nonadherence. Participants' demographic characteristics and baseline anthropometric measurements were reported as appropriately, mean and standard deviation or median and interquartile range for continuous variables, and frequency and percentages for categorical variables. The change in %BMIp95 between week 24 and baseline was assessed using analysis of variance (ANOVA) for all participants via ITT, per-protocol, PreCOVID and during COVID. First, the %BMIp95 was analysed in log scale mixed-effects linear regression model to assess the association between change in %BMIp95 and demographic characteristics (sex, ethnicity,

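### The six stated powers fit about 60 per arm and not the stated 292 youth, and the zBMI SD behind them is unstated, unsourced and hard to square with the stated correlation of 0.5

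*Combined protocol and SAP*

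**What the plan says.** All references are to the combined protocol and SAP. Under Power and Sample Size Estimates:

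- Size: "This study will enroll 292 patients and equally allocate into 3 groups".
- Basis for the SD of change: "conservation of correlation of 0.5 between pre and post measurements within each group", with two-sided 5% tests (ANOVA for aim 1, two-sample t-tests for aims 2 and 3).
- Aim 1 (three arms): at least 83% power for "the effect size of 0.244 with the variance of the group means of 0.0003 for the mean change of zBMI", and at least 89% for %BMIp95 at effect size 0.263 with a variance of means of 2.903.
- Aim 2 (AppCoach against Clinic): 88% for zBMI, where "an effect size of 0.580 corresponds to the mean difference of pre and post change in zBMI at least 0.040 standard deviation", and 92% for %BMIp95 at effect size 0.625 (4.08 points).
- Aim 3 (AppCoach against App): 71% for zBMI, where "an effect size of 0.464 corresponds to the mean difference of pre and post change in zBMI at least 0.032 standard deviation", and "a 68% power to detect an effect size of 0.452" for %BMIp95 (2.80 points).
- Conclusion: "Assuming 20% dropout rate, this study will achieve the desired study power of 80% for study aim 1 and 2".

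The Statistical Analysis section says that "180 participants (60 in each group) would provide 89% power", for %BMIp95 and with a different effect size (0.29). No SD for zBMI or for its change appears anywhere. The Outcomes section makes change in zBMI a primary outcome together with %BMIp95. Entry is at or above the 85th BMI percentile with no upper limit listed.

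**The concern.** A power figure follows from a sample size, an effect size and a test. Here all three are given, so the figures can be checked without outside input. If the powers belong to a different sample size, the sentence on which aims reach 80% has no clear basis. Aim 3 matters most: it isolates the value of coaching over the app alone, and the plan leaves it out of the aims said to reach 80%.

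The second issue concerns the effect sizes. Each is a difference divided by an SD of change that the plan never states. The section's own correlation lets a reader recover the between-participant zBMI SD, which looks very small for the eligible population. This is the only zBMI power statement in the document.

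**Working it through.** **Are the inputs read correctly?** Take the differences as zBMI units and set Clinic to 0. Then AppCoach is 0.040 and App is 0.040 − 0.032 = 0.008. The variance of these three means (divisor 3) is 0.000299, against 0.0003 stated. For %BMIp95 the means are 0, 1.28 and 4.08, with variance 2.903, as stated. The differences and variances form one consistent set.

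**Power by number per arm.** Aim 1 uses the noncentral F with three groups and λ = N·f². Aims 2 and 3 use the noncentral t with δ = d·√(n/2). All tests are two-sided at 5%. Numbers per arm:

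- 292/3 = 97.3
- after 20% dropout, 292 × 0.8/3 = 77.9
- 180/3 = 60
- 60 × 0.8 = 48

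| Per arm | zBMI, aims 1/2/3 (%) | %BMIp95, aims 1/2/3 (%) |
|---|---|---|
| Stated | 83 / 88 / 71 | 89 / 92 / 68 |
| 59 | 83.0 / 87.8 / 70.5 | 88.4 / 92.0 / 68.2 |
| 60 | 83.6 / 88.3 / 71.3 | 89.0 / 92.4 / 69.0 |
| 78 | 92.3 / 94.9 / 82.1 | 95.6 / 97.2 / 80.1 |
| 97 | 96.8 / 98.0 / 89.5 | 98.5 / 99.1 / 87.9 |
| 48 | 73.9 / 80.3 / 61.4 | 80.5 / 85.8 / 59.2 |

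The plan's figures are reproduced at 59-60 per arm, and at neither 97 nor 78. One-sided testing or a divided alpha does not bring the figures into line at 97 or 78. Dropout does not link the two sizes either: 180/0.8 = 225, not 292, and going from 292 to 180 is a 38% loss.

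**Which aims reach 80%.** At about 78 per arm, zBMI aim 3 reaches 82%. %BMIp95 aim 3 lies on the line: 80.1% at 78, and 79.9% with 233 completers (77.67 per arm). If 60 per arm were the enrolled number, 48 would remain and zBMI aim 1 would be 73.9%.

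**Implied SD of zBMI change.**

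- Aim 2: 0.040/0.580 = 0.069
- Aim 3: 0.032/0.464 = 0.069
- Aim 1: √0.0003/0.244 = 0.071 (0.065 to 0.077 allowing for rounding of the inputs)

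**Implied between-participant SD.** With equal pre and post SDs, SD of change = SD·√(2(1 − ρ)). At ρ = 0.5 the factor is 1, so the SD is also about 0.07. With unequal SDs s₁ and s₂, s₁² + s₂² − s₁s₂ ≥ 0.75·s₁², so s₁ is at most the SD of change divided by √0.75. That is 0.080 from 0.069, 0.082 from 0.071 and 0.089 from 0.077.

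**Assumed benchmarks (not document figures).** The 85th, 95th and 99th percentiles are z = 1.036, 1.645 and 2.326.

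- An even spread from the 85th to the 95th has SD (1.645 − 1.036)/√12 = 0.18.
- An even spread from the 95th to the 99th has SD 0.197.
- A standard normal cut at the 85th has SD 0.44.

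An SD of change of 0.069 would need ρ = 1 − 0.069²/(2·SD²), which is about 0.94 at SD 0.197 and 0.99 at SD 0.44.

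**The case against.** The mismatch is conservative. At 292 the stated effect sizes give more power than claimed, so the at-least wording for aim 1 remains true, and aims 1 and 2 reach 80% at 60, 78 and 97 per arm. They fail only for zBMI aim 1 at 48 per arm. That case treats 60 per arm as the enrolled number, which contradicts the section's own 292. All of this stands.

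Naming only aims 1 and 2 may also be defensible. The site totals under Study Design reach 292 youth only by counting the 12 pilot youth (190 + 12 + 3 × 30), who are excluded from analysis if the protocol is amended. Then 280 × 0.8/3 = 74.7 per arm, and aim 3 is 80.4% for zBMI but 78.3% for %BMIp95. This stands too, so the sentence cannot be called wrong for aim 3 as a whole; it needs an answer for each metric.

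On the SD, the document gives no zBMI SD, and every benchmark above assumes a distribution. An SD of change near 0.07 could be right, with only the 0.5 at fault. That limits the conclusion, but the stated inputs still need to be reconciled.

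Finally, the analysis text names only %BMIp95 for its ANOVA and mixed models, so the practical effect on zBMI may be modest. zBMI nevertheless remains a named primary outcome.

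**Conclusion.** The sample-size part is firm and rests only on the plan's own inputs: six of six stated powers fit 59-60 per arm, and none matches 292 before or after 20% dropout. The closeness to the 60 per group in the Statistical Analysis section suggests where the figures came from, but the document does not say so. At 292 the error understates power.

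The SD part is conditional. A between-participant zBMI SD of about 0.07 (up to about 0.08-0.09 with unequal SDs and rounding) follows from the stated inputs. That it is too small is a judgement, resting on the assumed spreads and on entry at or above the 85th percentile with no upper limit.

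A reader might infer that the trial is underpowered for zBMI. The document does not support that: a correlation well above 0.5 would make the SD of change credible, and nothing shows which input is at fault. Nor does it follow that 292 is too few, or that aim 3 is adequately powered on both metrics. The two problems may pull in opposite directions, so the net effect on true power is unknown.

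**What to change.** In Power and Sample Size Estimates:

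1. State the evaluable number per arm used, and reconcile it with 292, the 20% dropout and the 60 per group in Statistical Analysis. Say whether the 12 pilot youth are counted.
2. State the SD of change, or the SD and the pre-post correlation, with a source, so that these agree with one another and with the effect sizes.
3. Recompute and restate all six powers from those inputs, and rewrite the sentence on which aims reach 80% separately for zBMI and %BMIp95.

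The cost is a revision of text and figures in the power section, with a matching edit where 180 is cited, plus the work of finding a source. A stated power may become less favourable once the SD is sourced. No change to enrolment or outcomes is needed.

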During the second phase, which will overlap with the first, participants will eliminate snacking by choosing time periods to avoid snacking (i.e. morning, afternoon, or evening). Once the participant has abstained from snacking during their chosen time interval for 10 days, the participant will then choose additional time intervals to abstain from snacking, with the overall goal of abstinence from snacking between meals. In the third stage, excessive food amounts at meals will be targeted. Participants will weigh all food items served at meals, and an algorithm in the app will gradually reduce each participant's food amounts to result in 1 pound weight loss per week. Participants will take photos of meals via the app, post weighing, to allow for external confirmation of amount reduction. In addition, participants will have access to the app home page, which includes various addiction model strategies, including: motivation, distraction ideas, displacement methods and coping skills techniques⁷.

Participants in the AppCoach and App group will be asked to weigh themselves and food daily. All participations (AppCoach, App and Clinic) will receive monthly phone calls from the research team to speak with either the subject or the parent to review any barriers to adherence or technological problems that may have occurred with any of the study equipment. All phone conversations will be recorded.

Coaching (AppCoach group)

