The Clinic Intervention will utilize the Kids N Fitness Curriculum and will address the following topics over the 6-month intervention:

Session 1: Nutrition and Food Groups

Session 2: Portion Power

Session 3: Real Foods, Fat and Fiber

Session 4: Sugar Savvy

Sessions 5: Healthy Shopping, Healthy Eating

Sessions 6: Special Occasions and Moving Forward

Those youth randomized to the in-clinic control arm will complete the intervention at CHLA or virtually via WebEx. The participant and their parent/guardian will meet with each team member for 20-30 minutes to discuss the topic of the session. The youth will participate in some mild physical activity exercises, such as stretching. Treatment fidelity strategies will be utilized for all three intervention arms to ensure the accurate and precise delivery of each arm as intended. (See Treatment Fidelity Below).

Example Follow up Phone Calls Curriculum Outline (AppCoach):

Call	
1	Introduction: --Coach introduction --Curriculum introduction --Problem Food Identification --Goal setting
2	Personal Motivation: Identify personal motivation and goals of each participant. Have participant identify in and out of home barriers to weight management success. Problem Food Withdrawal Instruct to complete personal story
3	Problem Food Withdrawal -Assess barriers to compliance

4	Problem Food Withdrawal Progress
5	Introduce Snacking Elimination. Identify period of time to start withdrawal Problem Food and Snacking Withdrawal
6	Problem Food and Snacking Withdrawal
7	Problem Food and Snacking Withdrawal
8	Problem Food and Snacking Withdrawal
9	Continue PF and Snacking Withdrawal start food amount reduction Evaluate current barriers to weight management success. Have participant identify one goal to achieve over the next 4 weeks
	Introduce food weigh AppCoach and App: Distribute App setup instructional video
10	Progress report on above. Review frequency of eating out. Review missed weighed meals
11	Review progress, compensation and points earned. Identify successes and barriers. Make goals for second half of intervention
12	Review Face to Face / WebEx Visit 2 Goal of withdrawing from all 10 PF by week 12
13	Review maintenance PF avoidance. Encourage to consider assigning additional PF as tolerated
14	Goal of eliminating snacking by week 14
15	Review maintenance of PF and snacking avoidance

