The primary outcome will be change in zBMI and excess BMI percent over the 95th percentile (%BMI_{p95}) compared to baseline, assessed at 3, 6, 12 and 18 months, both within the groups and compared between groups and in clinic group. For analysis over time, the Δ%BMI_{p95} (BMI percentile – 95th percentile), which is the distance (in kg/m²) from the 95th percentile, will be utilized³¹.

Secondary outcomes will include: compliance with App intervention, retention rates with scheduled phone calls and clinic visits, ASRI, BRIEF, Satisfaction survey, YFAS-c, fasting lab testing compared pre and post intervention. Collected lab studies will include: HbA1c, Lipid Panel, AST/ALT. Each of these lab tests are currently recommended for routine clinical care screening every 6-12 months in obese adolescents³.

An estimated cost analysis will be completed to determine the cost per patient to implement the 6 month AppCoach intervention, App alone intervention and multi-disciplinary in-clinic intervention (Clinic)³². Cost Analysis to include: time or expenses saved compared to in-clinic (travel, missed work or school); efficiency of clinic and staffing needs, including appointment duration and physical space requirements, and health care utilization rates and costs of care^{33, 34}.

Analytic Plan:

Power and Sample Size Estimates:

The power analysis is prepared for comparing (1) the difference in the mean change of zBMI and %BMIp95 between baseline, 6 months, and 18 months across App+Coach, App, and Clinic, (2) the difference in zBMI and %BMIp95 mean change between App+Coach and Clinic, and (3) the difference in zBMI and %BMIp95 mean change between App+Coach and App. Review of the literature revealed that the majority of studies utilize the change in zBMI to evaluate the effectiveness of weight management interventions in adolescents. However, Freedman et al. and the CDC have proposed utilizing alternative metrics for weight change such as %BMIp95 which may be more strongly associated with change in body size in adolescents. Therefore, both metrics were considered in the power calculation to further explore their use as outcome measures in youth with obesity and severe obesity.

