obesity related co-morbidities), CED-SC, PSS, BRIEF-2, YFAS-c, and BEDS-7 scores univariately and adjusting for recruitment site as a covariate. Then, a multivariable mixedeffects linear regression model was utilized to examine the effect of the possible factors on change in %BMIP95 accounting for recruitment site, demographic and other measured characteristics. The results are expressed in percent change with its associated 95th% confidence interval and p-value.

Data management and quality assurance

Principles underlying our approach to quality control includes: (1) standardization of measurements; (2) use of clear and specific protocols for all study activities including training for data collection and processing; (3) validation and verification of data management procedures by using of software capable of checking for out-of-range values and other sources of outliers; (4) implementation of a data cleaning protocol; and (5) periodic meetings and progress reports to provide specific, well-documented feedback to the investigators concerning potential difficulties as well as sufficient follow-up to ensure that problems are resolved in a timely fashion. Confidentiality will be strictly maintained during all data management. Children's Hospital of Los Angeles Biostatistics Core, Saban Research Institute, will follow aforementioned schemes to collect and manage with maintaining consistent quality and security of the study observations.

Data Collection Management Plan AppCoach:

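### Missing at random does not justify LOCF, which is the only stated method for missing week-24 %BMIp95 in the ITT comparison and can distort it

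*Combined protocol and SAP*

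**What the plan says.** The Outcomes section makes change in zBMI and %BMIp95 primary, "compared to baseline, assessed at 3, 6, 12 and 18 months". In the Statistical Analysis section:

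- The analysis assumes that "data are missing at random, therefore, imputation using last observation was carried forward".
- The only other imputation is restricted: "multiple imputation based on logistic regression model (for BEDS-7 scores only) were utilized to account for missing data".
- The comparison is a week-24 analysis: "The change in %BMIp95 between week 24 and baseline was assessed using analysis of variance (ANOVA) for all participants via ITT", and also in the per-protocol, pre-COVID and during-COVID sets.
- The one stated check on the imputation is this: "Results from the ITT analysis using imputation were compared as per protocol analysis with completed data".
- Mixed models follow. They relate %BMIp95 to demographic characteristics and questionnaire scores, adjusting for recruitment site; the multivariable "linear regression model was utilized to examine the effect of the possible factors on change in %BMIP95". Arm is not named as a term, and the text does not say whether imputed data enter these models.

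The section does not say which observation is carried forward. The Power and Sample Size Estimates section assumes 20% dropout overall and gives no rate by arm.

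**The concern.** MAR and LOCF are different assumptions. MAR says that, given the observed data, whether a value is missing does not depend on the value itself. Missing week-24 values can then be predicted from participants with the same history who stayed. LOCF says something else: that dropouts, on average, do not move after their last measurement. The first can hold while the second fails, so the plan's own assumption gives no support to its method.

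At stake is the ITT comparison of a primary outcome. If dropout or later change differs between arms, LOCF can create a difference that does not exist. If dropout is equal and the arms truly differ, LOCF dilutes the difference. The mixed models do not repair this, because as described they estimate associations with participant characteristics and not an arm contrast at week 24.

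**Working it through.** **Inputs**

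| Input | Value | Source |
|---|---|---|
| SD of change in %BMIp95 | 4.08 / 0.625 = 6.53 | Power and Sample Size Estimates |
| Participants per arm | 60, or 292 / 3 = about 97 | Statistical Analysis; Power and Sample Size Estimates |
| Overall dropout | 20% | Power and Sample Size Estimates |
| Dropout by arm | 10/20/30% | Assumption, averaging 20% |
| Common mean change to week 24 | -4.08 to +2 points | Assumption; 4.08 is borrowed from the planned between-arm difference |

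This point contests no stated figure. As a check on the SD, the section's ANOVA inputs give √2.903 / 0.263 = 6.48, and its App+Coach versus App inputs give 2.80 / 0.452 = 6.19.

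**Step 1. Error of LOCF.** Let d be the share of an arm missing at week 24, and g the mean change in those participants from the last observation to week 24. LOCF sets g to zero, so the arm mean is off by -d·g, and the contrast A minus B is off by

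-(dA·gA - dB·gB).

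This vanishes if g is zero, or if d·g is equal in the two arms. MAR guarantees neither.

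**Step 2. Numbers under no true difference.** Compare the best-retained arm (10%) with the worst-retained arm (30%); a negative value favours the better-retained arm.

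- Baseline carried, g = -4.08: -(0.10 × -4.08 - 0.30 × -4.08) = -0.82.
- Value halfway to week 24 carried, g = -2.04: -0.41.
- Baseline carried, g = -2: -0.40. With g = +2: +0.40.
- Equal dropout: 0.

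**Step 3. Type I error when dropout is random within arm.** Three-arm simulation, ANOVA at 0.05, 10/20/30% dropout:

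| Common change | Value carried | False difference | Type I error (60 / 97 per arm) |
|---|---|---|---|
| -4.08 | baseline | 0.8 | 9.1% / 12.5% |
| -4.08 | halfway | 0.4 | 6.1% / 6.5% |
| -2 | baseline | 0.4 | 6.0% / 6.8% |
| -2 | halfway | 0.2 | 5.0% / 5.4% |
| 0 | either | 0 | about 5% |
| +2 | baseline | 0.4, reversed | 6.2% / 6.7% |

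Here the completed-data comparison is unbiased, so setting it beside LOCF would reveal the gap.

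**Step 4. Dropout that depends on the month-3 result (MAR).** Further assumptions: month-3 change has half the week-24 mean, SD 6.53 and correlation 0.7 with week-24 change; the log-odds of later loss rise 0.7 per SD of a worse month-3 result; realised dropout is about 12/22/32%. Month 3 is carried. No true difference, common change -4.08:

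| Estimate | Error (60 / 97 per arm) |
|---|---|
| LOCF | -0.56 / -0.53 |
| Completers | +0.55 / +0.59 |
| Week 24 regressed on month 3 within arm (MAR-based) | -0.01 / +0.02 |

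Type I error is about 6-8% for LOCF and for completers, and about 5% for the MAR-based estimate. LOCF and completers err in opposite directions and lie more than 1 point apart, so the planned comparison would signal a problem but could not say where the truth lies. With no overall mean change, LOCF is still off by about -0.1: dropouts were selected for a poor month-3 result, and part of that would have regressed by week 24.

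**Step 5. Equal 20% dropout with a true difference of 4.08.** With baseline carried the expected estimate is 0.8 × 4.08 = 3.26; with halfway, 0.9 × 4.08 = 3.67. Power suffers little: with baseline carried, 76-79% against 80% in completers at 60 per arm, and 94-95% against 95% at 97 per arm.

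**The case against.** **The carried value may be fresher than month 3.** The protocol collects other weights: daily weighing in the app arms, a weight at each monthly Clinic session, and weight outcomes in monthly calls to all arms. If a month-5 value were carried and change were linear, the remaining change would be 4.08 / 6 = 0.68, and the 10/30% case would shrink to 0.20 × 0.68 = 0.14 points. This stands as a limit on size. But the plan does not say that these weights are used, does not describe height measurement between visits in the app arms, and collects weights at different frequencies by arm.

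**The completed-data comparison would expose the problem.** In step 3 it would. In step 4 it would raise the alarm without settling the matter. The largest error rates belong to step 3 only; no scenario here combines them with a check that misleads.

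**The MAR-based estimate succeeds by construction.** True: step 4 generates MAR data and analyses them under MAR. It shows that LOCF can fail when the plan's own assumption holds, and does not show that the assumption is realistic.

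**Stronger readings that the documents do not support.**

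- A reader might infer that dropouts in the app arms would have gone on losing weight, because the app reduces "food amounts to result in 1 pound weight loss per week" and the example call outline places "Continue PF and Snacking Withdrawal start food amount reduction" at call 9 of 24. These passages describe intended loss in participants on the intervention; nothing describes weight after loss to follow-up.
- A reader might infer from the pilot's retention (100% against 37%) that Clinic will lose more participants here. That comparison was self-selected and not randomised. It shows that unequal dropout is possible, and does not predict it.
- A reader might infer that the trial's result is wrong. Without dropout by arm and the later course of dropouts, neither the direction nor the size of any distortion can be stated.

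**Conclusion.** The concern holds as a fault of reasoning with a practical consequence. The plan derives LOCF from MAR, which does not support it, and states no other method for missing week-24 %BMIp95 in the ITT comparison. Confidence is high in that error and in the remedy, not in the size.

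The illustrations run from no distortion to 0.8 points with 9-12.5% type I error. The upper end needs a 20-point dropout gap between the extreme arms, a change of -4.08 and baseline carried, and is near the worst case examined. Most other scenarios with unequal dropout give about 5-7%. All of this rests on assumed dropout by arm and assumed change; only the SD, the group sizes and the 20% overall dropout come from the plan. It should be fixed, because a primary comparison ought to rest on the assumption the plan states.

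**What to change.** Make the primary analysis of week-24 %BMIp95 valid under MAR, using the scheduled month 0, 3 and 6 data, by one of:

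- a likelihood-based repeated-measures mixed model with arm, visit, arm-by-visit and baseline, reporting the week-24 arm contrasts; or
- multiple imputation by arm, with the month-3 value in the imputation model.

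Apply the same to zBMI if it is analysed in the same way. Keep LOCF only as a labelled sensitivity analysis that defines the observation carried, including whether interim and self-reported weights count. Report dropout by arm. A delta-adjusted analysis for departures from MAR is optional.

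The cost is SAP wording, code, and re-analysis if results already exist (the section is written in the past tense). The standard error of the arm difference rises modestly, roughly 3-10% over LOCF in simulation (for example from 1.25 to 1.31 at 60 per arm), under the assumed correlation of 0.7 between month 3 and week 24. No new data are needed.
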